6.3 Pre-enrollment screening

- A. Tumor Characteristics
 - 1. A core biopsy or excisional biopsy demonstrating IBC.
 - 2. A standard clinical HER-2/neu immunohistochemical stain and FISH test will be performed using the Hercept test (Dako) on specimens obtained by core biopsy material or resected tumor.
 - 3. A standard clinical ER, PR test.
- B. Baseline patient evaluation
 - 1. All subjects will have a baseline history and physical exam.
 - 2. Laboratory work-up will consist of:
 - a) CBC w/ differential
 - b) PT/PTT
 - c) electrolytes-Na/K/Cl/CO₂/BUN/Cr/glucose
 - d) liver function tests
 - e) urinalysis
 - f) Beta-HCG serum (for all pre and perimenopausal women)
 - g) EKG
 - h) HLA typing (to be obtained as part of study)
 - i) MUGA or Echocardiogram (Must have 50% EF)
 - j) Blood for immune analysis (6 tubes)
 - 3. Baseline radiologic evaluation
 - a) Mammogram up to six months prior to consenting to participate in the study will be acceptable. (Unilateral or bilateral if bilateral mastectomies mammogram not needed)

- b) CT scans of the chest abdomen and pelvis or PET/CT within 60 days of enrollment
- C. Performance of the Pre-screening tests

All of the pre-screening tests will be obtained by the patient prior to first treatment.

1. Histopathologic Testing of Tumor

Subjects will have undergone core or resection of primary tumor prior to enrollment in this protocol to confirm diagnosis of IBC. The Hercept (Dako) antibody will be used to analyze the expression of HER-2/neu on the IBC. Conventional HER-2 3+ 10% of the cells will be considered classic HER-2 positive or 2+ with FISH amplification 2 fold increase in FISH amplicons. For HER-2 2+ FISH negative, ten percent of the cells staining at least 2+ will be considered positive for HER-2/neu expression.

6.1 Preparation of the vaccine

Preparation of the vaccine is a multi-step process starting with leukapheresis and countercurrent centrifugal elutriation to obtain the relevant monocyte pool. This monocyte pool will then be treated with GM-CSF then pulsed with HER-2/neu peptides and finally matured with INF- γ , and LPS for conversion into type 1 dendritic cells (DC1). When occurring at University of Pennsylvania a study monitor will oversee quality assurance of vaccine production. When occurring at Moffitt Cancer Center, all standard institutional quality assurance policies will be followed.

6.1.1 Subject Leukapheresis

Subjects will first undergo leukapheresis to obtain lymphocyte and monocyte fractions. The leukapheresis will be performed in the pheresis facilities at the University of Pennsylvania or at Moffitt Cancer center by certified personnel. Subjects will be apheresed 15-20 liters whole blood on a Gambro Spectra or equivalent apparatus. We expect to be able to generate $1-5x10^{10}$ PBMC. In the event a subject has poor peripheral access, the option of having an internal jugular line

Pilot Phase I HER-2 Pulsed DC Vaccine to Prevent Recurrence for Patients with HER-2 Driven High Risk Invasive Breast Cancer placed by the interventional radiology division will be offered as an alternative. At the time of the apheresiscollection, a tube of serum will be drawn and tested for a baseline anti-HER-2/neu response. This will then be compared with a specimen of serum that will be taken and tested post vaccine.

For subjects in whom leukapheresis did not yield sufficient number of cells to make all 6 vaccines and 3 booster vaccines $(1.8 \times 10^{9} \text{ monocytes})$, an additional apheresis collection will be undertaken to yield enough cells to manufacturer the remaining vaccines.

Subjects may additionally undergo leukapheresis (15-20 liters) at the completion of the first 6 vaccines to obtain adequate numbers of the T lymphocyte population for immunologic analysis, as well as to obtain lymphocyte and monocyte fractions to produce 3 booster vaccines. For subjects in whom the initial and second leukapheresis did not yield sufficient number of cells to make all 6 vaccines and 3 booster vaccines, an additional pheresis may be undertaken. At the completion of pheresis all IV access will be removed.

Subjects will have 5mL of peripheral blood drawn at multiple time points during the vaccine schedule (pre vaccine, post six vaccines, pre booster 1, pre booster 2, pre booster 3, and completion of all vaccinations) to monitor immunologic responses to the administered vaccines. Subjects will also have the option to undergo additional leukapheresis (10-15 liters) at the completion of the 6 vaccines or completion of the three boosters to obtain T lymphocyte population for additional immunologic analysis.

6.1.2 Elutriation

To separate the lymphocyte and monocyte fractions, the apheresis product obtained will then be subject to countercurrent centrifugal elutriation on a Model J-6M centrifuge (Beckman Instruments) equipped with a JE-5.0 elutriation rotor operating at 1725g and 20°C) or equivalent apparatus. The apheresis product is loaded onto the elutriator at 120cc/minute flow rate, then fractions are collected using stepwise increases in flow rates to obtain lymphocyte-rich (120 and 140 cc/minute), transitional (150 cc/minute) and monocyte-rich (180 and 190 cc/minute) fractions. A final monocyte-rich fraction is collected at zero rpm (rotor off). Lymphocyte- rich fractions are then further purified with density gradient centrifugation using Ficoll-Hypaque to remove the red blood cells.

The monocyte fraction is washed, counted and aliquoted out into portions for individual vaccines and cryopreserved for use at a later date.

6.4.3. Cell culture and preparation of dendritic cell vaccine (Table 1)

All elutriation will be performed in the FDA-approved facilities in the blood bank. All work here in the production of the monocytes will be performed following strict guidelines for sterility and will be done with Good Laboratory Practices. [name], Supervisor in the Cell Processing Center will oversee elutriation at University of Pennsylvania and [name] will oversee elutriation at Moffitt Cancer Center. The vaccine activation will take place in the FDA approved facility in the Clinical Cell and Vaccine Production Facility (CVPF) in Maloney 6 of the Hospital of the University of Pennsylvania, or at the Cell Therapy Facility (CTF) at Moffitt Cancer Center, under Good Manufacturing Practices. The CVPF and CTF are both accredited by the Foundation for the Accreditation of Cellular Therapy (FACT). Pilot Phase I HER-2 Pulsed DC Vaccine to Prevent Recurrence for Patients with HER-2 Driven High Risk Invasive Breast Cancer For those subjects transferring from University of Pennsylvania and receiving vaccines at Moffitt Cancer Center, elutriated product will be shipped cryopreserved and monitored using standard shipping methods already in place at the Cell Therapy Facility at the Moffitt Cancer Center. Those elutriated monocytes will be stored cryopreserved and activated into DC as described below. Any subjects newly enrolled at Moffitt Cancer Center will have elutriated product generated in the Cell Therapy Laboratory at Moffitt Cancer Center. Any subject receiving vaccine or boost at Moffitt cancer center will be a registered patient of Moffitt Cancer Center.

Monocytes will be washed 2 times in Hanks Buffer. Monocytes will be cultured with GM-CSF, IL-4, IFN- γ , and LPS for conversion into DC1. Monocytes at concentrations of 3×10^6 cells/ml will be cultured in serum free medium (Gibco BRL, Grand Island, NY) with 50 ng/ml (250 IU/ml) rhGM-CSF, and IL-4 1000 u/ml (R&D Systems, Minneapolis, MN) and 20 ug/ml HER-2/neu peptides will be added to the culture on the morning of day 2. If, after thawing the cryopreserved cells, there is less than 85% cell viability, the exact number of cells needed for vaccine production will be cultured for one extra day in rhGM-CSF and vaccine administration will be moved back one day. Recombinant HER-2/neu peptides **3 ECD** p42-56 (HLDMLRHLYOGCOVV), p98-114 (RLRIVRGTOLFEDNYAL), p328-345(TORCEKCSKPCARVCYGL) and 3 ICD p776-790 (GVGSPYVSRLLGICL), p927-941 (PAREIPDLLEKGERL) and p1166-1180 (TLERPKTLSPGKNGV) (American Peptide Co. Sunnyvale, CA) will be pulsed on day 2. The peptides will be pulsed in separate wells 2-3 wells per peptide to avoid competition for binding in the MHC. The evening of day 2 IFN-y (1000 u/ml) will be added. Six - eighteen hours later LPS (10 ng/ml) will be added and the cells cultured an additional 2-8 hours. For HLA-A2+ subjects, one hour prior to harvest, pulse DC1 in addition to above with 50ug/ml of HER-2/neu class I binding peptides into one well of each ECD and ICD with two different peptides (369-377, 689-697). For HLA-A3+ subjects, one hour prior to harvest, pulse DC1 in addition to above with 50ug/ml of HER-2/neu class I binding peptide into one well of each ECD and ICD with one peptide (369-377). In the event that HLA-A tissue typing results that have not been completed in time for the HLA-A2 peptide addition, will have the peptides added to the culture under the principle that if said patient is not HLA-A2+ or HLA-A3+ the peptides will not be able to bind properly and be washed away during the harvest of the vaccine. The cells will then be harvested from the plates, washed three times with Hanks Buffer, counted and pooled. Viability will be determined by trypan blue exclusion. About 2 to 2.5 million DC1 from each peptide specificity will be pooled so that a total vaccine number of about 1.0-2.0 x 10⁷ cells resuspended in 20cc sterile saline. From this 20cc 5cc will be removed for gram stain, sterility testing, endotoxin testing and FACS analysis. These tests will be performed with this 5cc solution. The remainder of the cells, about 10-20 million cells, will be centrifuged and the pellet resuspended in 1ml for administration. The final vaccine solution will be labeled with the subject's name, date and time prior to release. The vaccine will be administered shortly after preparation. Long term, > 4 hour, storage of the vaccine is not anticipated. Short term storage of the vaccine at 4^oC will be accommodated for 4-6 hours after which the vaccine will be discarded if not used. The vaccine prepared will be stored in the administration syringe 1cc tuberculin syringe at 4^oC and will be directly administered to the subject nodes. A 22 or 23 gauge needle will be used for injection to prevent cell lysis.

A sample of each vaccine will be sent for endotoxin testing, gram stain, and Bac Tec and broth sterility cultures. An aliquot of the clinical product will be submitted to the Department of Microbiology or to the Cell Therapy Quality Control Lab at Moffitt Cancer Center and they will prepare a smear for gram stain testing. In addition, two tubes (or BacTAltert blood culture bottles at Moffitt) will be inoculated and this will be sent to the Department of Microbiology or to the Cell Therapy Quality Control Lab for sterility testing A negative gram stain of the

Pilot Phase I HER-2 Pulsed DC Vaccine to Prevent Recurrence for Patients with HER-2 Driven High Risk Invasive Breast Cancer vaccine sample will be

required in order to clear the vaccine for subject administration. The endotoxin test will be performed according to Good Laboratory Practices in the CVPF. The results of endotoxin testing and microbiology cultures will be checked when available and if not meeting specifications the vaccine will be discarded. An endotoxin level of less than 5 EU/kg body weight will be accepted. Sterility testing will be performed in accordance with CFR 610.12 and a specification of no growth will be required. A final quality analysis certificate will be issued for each dose of vaccine administered. (Appendix B). Additionally, cell viability of the prepared vaccine will be determined using trypan blue staining. The results will be available prior to vaccine administration. Cell viability of >70% will be required for release of vaccine. If this cutoff is not met, then the vaccine will be re-made. In addition, a sample of each vaccine will also be removed for FACS analysis of cell surface markers to confirm conversion of monocytes to DC. Since the activity of the vaccine does not depend on phenotype the vaccine will not be held for phenotype but will serve as an internal evaluation of the process of vaccine preparation (see below).

The requirements for vaccine release then are:

Viability	>70%
gram stain result	no organisms
endotoxin test	<5EU/kg subject weight
culture and sensitivity	no growth final culture

Since the culture test will become available after vaccine administration the following contingency plan will be in place for a positive culture:

- Notification of both the primary attending physician and the subject.
- Identification of the responsible microorganism and sensitivity testing.
- A description of additional subject monitoring as required by the circumstances of the contamination incident.
- Initiate an investigation of the event and take corrective actions to prevent future recurrences. The scope of the investigation and proposed corrections should include:
 - Evaluation of your current procedures for collecting and processing the autologous peripheral blood product to determine the step at which contamination could be introduced.
 - Development of changes in the procedures that will assist in preventing sterility lapses in the future.
 - Development of appropriate testing to ensure that revised changes to the procedures produce a sterile product. This should include sterility testing at various points in the preparation of the product.
- Report the incident as an adverse event to the agency within 15 working days.

The first vaccine may be made from freshly collected and elutriated or cryopreserved cells. Subsequent vaccinations will be made from cryopreserved aliquots. At the University of Pennsylvania, once thawed, these cells will be washed with medium twice prior to their placement in culture. At Moffitt Cancer Center, an individual vial will be removed from liquid nitrogen and allowed to thaw to room temperature. Once vial is fully thawed, the vaccine will be transferred from the vial into a syringe for injection. The thawed vaccine will be stored at a cool temperature, around 4 degrees C.

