3. Add rhGM-CSF for final concentration of 50 ng/ml or 250 IU/ml and IL-4 1000 u/ml (see IV Preparation of Reagents). Culture overnight. If, after thawing the cryopreserved cells, there is less than 85% cell viability, the exact number of cells needed for vaccine production will be cultured for one extra day in rhGM-CSF and vaccine administration will be moved back one day.

4. The next morning, add HER-2/neu peptides for a final concentration of of 20μ g/ml 3 ECD - 56, p98-114, p328-345 and 3 ICD p776-790, p927-941 and p1166-1180 These will be pulsed in separate wells.

5. In the afternoon, add IFN- γ 1000 u/ml, culture cells at 37°C and 5% CO2 overnight for 14 hours.

6. The following morning, add LPS (10 ng/ml)

7. Incubate 2-8 hours.

8. For HLA-A2+ subjects, one hour prior to harvest, pulse DC1 in addition to above with 50 ug/ml HER-2/neu class I binding peptides into one well of each ECD and ICD with two different peptides (369-377 and 689-697). For HLA-A3+ subjects, one hour prior to harvest, pulse DC1 in addition to above with 50ug/ml of HER-2/neu class I binding peptide into one well of each ECD and ICD with one peptide (369-377). In the event that HLA-A tissue typing results have not been completed in time for the HLA-A2 peptide addition, will have the peptides added to the culture under the principle that if said patient is not HLA-A2+ or HLA-A3+ the peptides will not be able to bind properly and be washed away during the harvest of the vaccine.

9. Harvest cells into 50cc Falcon tubes. Maximum 20 cc cell volume and add 20 cc Hanks Buffer and spin at 1200 rpm for 5 minute @ 22^{0} C. Repeat this step, wash the cells again.

10. Aspirate supernatant. Remove 20μ l for cell count to estimate % cell death. Pool 2-2.5 million cells per each peptide and respin cells at 1200 rpm, 22^{0} C for 5 minutes. Resuspend in 20cc sterile saline. Remove 12-18 million cells, about 15cc, for vaccine preparation and from the 5cc remaining the tests of endotoxin, sterility testing, gram stain and FACS (see 6.5.4 Phenotypic Analysis of DC1) will be obtained. The vaccine component will be centrifuged and resuspended to 1cc with a total cell number 1.0-2.0 x 10^{7} cells.

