6.4.6 Administration of the Vaccine

A. Selection of Lymph nodes for vaccination

Ultrasound will be used to identify non-pathologic lymph nodes in the groin as first choice or axilla as second choice. Non-pathologic nodes by ultrasound criteria have a fatty hilum and will

be selected; two nodes per vaccine preferentially 1 node per groin. If a patient has lymphedema or prior groin dissection on a single side then the contralateral groin will be used or alternatively the axilla. Often we only are able to identify 1-2 nodes in the groin by ultrasound. Nodes without a fatty hilum that have evidence of pathologic disease will be excluded from injection.

B. Administration of the initial Vaccine

Vaccines will be labeled (for example, with the subjects study ID, study initials, date and time) prior to release. The patient will be seen by the PI or designee, and Research Coordinator and a history and physical exam will be performed. Ultrasound (US) guided intranodal delivered vaccines will be administered in the NIH Clinical Research Center at Penn or the Clinical Research unit at Moffitt Cancer Center by a radiologist or sonographer experience in ultrasound guidance and the

principal investigators or his/her designee. Each dose will consist of between $1.0-2.0 \times 10^7$ cells and will be injected into 1-2 different normal groin lymph nodes or axillary nodes.

C. Post vaccine assessment

Subjects will be administered the vaccine and observed. All subjects with vaccine related AEs will be followed until the AE has resolved to baseline. Vital signs will be obtained prior to the vaccination and again 15 minutes after the dose is given. Subjects with no noted complications will be then discharged. The anticipated complication could be fever. If an adverse reaction is observed, the subject observation time will be revised appropriately. A physician familiar with the study will be readily available in the event of any complication and such subjects will be transferred to an appropriate care unit for further monitoring and treatment Similarly any discharged subject who develops symptoms will be promptly re-evaluated and admitted for care if inpatient hospitalization is deemed necessary by the principal investigator or his/her designee.

D. Vaccine Schedule

The vaccine schedule is meant to be weekly; however the first 6 vaccines may be given anywhere between 8-21 days apart.

E. Vaccine Tolerance

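### The cell counts in 6.4.3, Table 1 step 10 and 6.4.6 do not agree: the written pooling and sampling steps give 9.0–11.25 million cells, against 12–18 million and 10–20 million stated

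*Combined protocol and SAP*

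**What the plan says.** The number of cells in a vaccine is set out in three places.

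- **Section 6.4.3 (text).** The pooling line reads "About 2 to 2.5 million DC1 from each peptide specificity will be pooled". The pool is described as a "total vaccine number of about 1.0-2.0 x 10⁷ cells resuspended in 20cc sterile saline". A 5 cc portion of the 20 cc is then taken for quality-control testing, after which: "The remainder of the cells, about 10-20 million cells, will be centrifuged and the pellet resuspended in 1ml for administration".
- **Table 1, step 10.** The per-peptide count is the same: "Pool 2-2.5 million cells per each peptide", again brought to 20 cc. The next instruction is "Remove 12-18 million cells, about 15cc, for vaccine preparation", with the other 5 cc going to testing. The step ends with a final count of 10–20 million in 1 cc.
- **Section 6.4.6.** For all six vaccines and all three boosters the wording begins "Each dose will consist of between" and gives 10 and 20 million cells as the limits.

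There are six class II peptides, three ECD and three ICD, kept apart in culture: "p98-114, p328-345 and 3 ICD p776-790, p927-941 and p1166-1180 These will be pulsed in separate wells" (Table 1, step 4). HLA-A2+ subjects also receive "HER-2/neu class I binding peptides into one well of each ECD and ICD with two different peptides (369-377, 689-697"; HLA-A3+ subjects receive one such peptide.

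Section 6.4.3 lists four release requirements: viability, gram stain, endotoxin and culture. The release and remake conditions in Table 1 steps 11 and 12 name no cell count either.

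**The concern.** The per-peptide count, the number of peptides and the share of volume kept together fix the number of cells left for injection. That number matches neither of the other two figures. Staff following the pooling line literally would prepare a product that cannot contain what the next instruction in the same table step says to take from it. At the low end it would fall under the dose limit in 6.4.6.

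Cell number defines the exposure that the safety results (primary) and immune results (secondary) describe. A reader of those results needs to know what was given, and at present the protocol offers three different answers. Since no listed release criterion checks cell number, the listed criteria would not catch a low count.

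**Working it through.** **Inputs**

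| Quantity | Value | Source |
|---|---|---|
| Cells pooled per peptide | 2–2.5 million | 6.4.3; Table 1 step 10 |
| Peptide specificities | 6 | 6.4.3; Table 1 step 4 |
| Pool volume | 20 cc | 6.4.3; Table 1 step 10 |
| Volume removed for testing | 5 cc | 6.4.3; Table 1 step 10 |
| Fraction kept | 15/20 = 0.75 | arithmetic |
| Wells plated | 12–18 (60–80 at Moffitt), 1 cc each at 3 million/ml | Table 1 step 1 |
| Wells per peptide | 2–3 | 6.4.3 |
| Retrieval at harvest | 50–75% | Table 1 step 1 |

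The count of six agrees with the plan's own well count: 6 × 2 = 12 and 6 × 3 = 18 wells.

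**1. Trying to reproduce the stated 10–20 million after sampling.**
Pool = 6 × 2.0 to 6 × 2.5 = 12–15 million.
Left for injection = 0.75 × 12 to 0.75 × 15 = **9.0–11.25 million**.
The stated range is not reproduced; the overlap is 10–11.25 million. The shortfall at the low end is (10 − 9)/10 = 10%.

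**2. Section 6.4.3 against itself.**
If the 20 cc holds 10–20 million, the 15 cc holds 0.75 × 10 to 0.75 × 20 = 7.5–15 million. One range cannot be right both before and after a quarter is removed.

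**3. Table 1 step 10 against itself.**
To have 12–18 million in 15 cc, the pool must be 12/0.75 to 18/0.75 = 16–24 million, or 16/6 to 24/6 = 2.67–4.0 million per peptide. This does not overlap 2–2.5 million. Equivalently, the derived maximum (11.25 million) is below the stated minimum (12 million).

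**4. Per-peptide count implied by the dose in 6.4.6.**
10/0.75/6 = 2.22 million for the floor and 20/0.75/6 = 4.44 million for the ceiling. Of the written 2–2.5 million, only 2.22–2.5 million reaches the floor.

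**5. Does the culture yield enough cells?**
12 × 3 × 0.50 = 18 million, up to 18 × 3 × 0.75 = 40.5 million harvested. After a quarter is removed: 13.5–30.4 million. At 60–80 wells the harvest is 60 × 3 × 0.50 = 90 to 80 × 3 × 0.75 = 180 million. So the stated range is within reach if more cells are pooled. If 50–75% is instead taken as the loss (an assumption; the plan calls it retrieval), the harvest is 12 × 3 × 0.25 = 9 to 18 × 3 × 0.50 = 27 million, or 6.75–20.25 million after sampling.

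**6. Sensitivity to the number of specificities.**
If class I peptides counted as separate pools:
- seven give 14–17.5 million pooled and 10.5–13.1 million for injection;
- eight give 16–20 million pooled and 12–15 million for injection.

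**The case against.** The strongest reply is that the mismatch is small and confined to one intermediate figure. The dose is a range, so a product of 11 million complies with 6.4.6. Table 1's 12–18 million also lies wholly inside 10–20 million. The counts in 6.4.3 are approximate, and the worst shortfall is 1 million cells. Cells are plated in excess and counted at harvest, so staff can correct the number. The final count in step 10 could be treated as the working requirement.

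Most of this stands, and it rules out several stronger readings that a reader might infer:

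- *That the process cannot make the stated dose.* It is not shown. The derived range overlaps the stated one, and the harvest is ample.
- *That the gap is two-fold.* This treats the top of a permitted range as a target. Nothing requires 20 million.
- *That safety and immune results will describe the wrong dose.* This does not follow. There are no dose levels, no analysis in 6.9 uses cell number, and 6.7 D attributes toxicity to the preparation process as a whole.
- *That the two sites will give different doses because of these lines.* Neither the pooling sentence nor step 10 is assigned to a site.

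Two parts of the reply do not succeed. Approximation cannot join 9.0–11.25 and 12–18 million, which do not overlap within a single table step. Counting class I peptides as extra pools would bring the product inside 10–20 million, but they go into wells already holding an ECD or ICD peptide. Nor would it help subjects who receive no class I peptide; 6.8 B expects HLA-A2.1 in only about 25%.

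**Conclusion.** The point holds as an inconsistency between written figures. On six specificities, 2–2.5 million cells each and 5 of 20 cc removed, the product is 9.0–11.25 million cells. That is below all of Table 1's 12–18 million and up to 10% below the 6.4.6 minimum. Section 6.4.3 also repeats one range on both sides of a 25% removal. With no cell count among the listed release requirements, a dose under the stated minimum could pass them.

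The result rests on the cells being evenly suspended, so that a quarter of the volume carries a quarter of the cells, and on six pools. At seven or eight pools the 10 million floor is met. At eight the result, 12–15 million, also falls inside Table 1's range.

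The plan does not say whether its range means total or viable cells. At the 70% viability limit, 9.0–11.25 million total cells would be about 6.3–7.9 million viable (0.70 × 9.0; 0.70 × 11.25). This shows why the basis should be stated; it is not a further contradiction.

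This should be fixed, but it does not undermine the analysis: no endpoint, stopping boundary or confidence interval in 6.9 changes. The documents do not show which figures are intended.

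**What to change.** 1. Reconcile the per-peptide count, pooled count, volume removed and final count across 6.4.3, Table 1 step 10 and 6.4.6 so that they multiply through. The sponsor decides which figures are intended.
2. State whether the range refers to total or viable cells, and whether it is counted before or after the test sample is removed.
3. Say how a count outside the stated range is handled at release, since the listed requirements do not address it.
4. Report the delivered count for each dose alongside the safety and immune results. The count may already be on the quality analysis certificate that 6.4.3 requires for each dose (Appendix B, not in the text available here). If so, the counts for the fifteen subjects already enrolled can be taken from existing records.

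The cost is protocol wording and at most one case report form field. No extra subjects or procedures are needed.
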